4.4.1.3 Supportive Analyses

N/A

4.4.2 Secondary Efficacy Variables

See Section 4.5.

4.4.3 Handling of Missing Values/Censoring/Discontinuations

Missing data will not be replaced or imputed. Dropouts will be included in analyses up to the point of discontinuation.

4.5 Analysis of Secondary Objectives

The mITT population will be considered as primary population for secondary analyses.

4.5.1 Efficacy (Secondary)

The secondary efficacy endpoints are:

- Mean RPI_{overall} (Day 7 pre- and post-brushing, Day 28 pre- and post-brushing)
- Mean TPI_{overall} (Day 7 pre- and post-brushing, Day 28 pre- and post-brushing)
- Mean RPI_{gingival margin} (Day 0 pre- and post-brushing, Day 7 pre- and post-brushing, Day 28 pre- and post-brushing), defined as mean RPI score for sites A, B and C
- Mean RPI_{inter-proximal} (Day 0 pre- and post-brushing, Day 7 pre- and post-brushing, Day 28 pre- and post-brushing), defined as mean RPI score for sites D and F
- Mean TPI_{inter-proximal} (Day 0 pre- and post-brushing, Day 7 pre- and post-brushing, Day 28 pre- and post-brushing), defined as mean TPI score for mesial and distal sites

Secondary outcome variables will be derived, based on relevant tooth sites, as the primary outcome variables.

Summary statistics (n, missing, mean, SD, SE, median, minimum, maximum) of pre-brushing, post-brushing and change from Day 0 pre-brushing will be presented for each secondary outcome variable at each assessment time point by study product group in the following tables:

- [Table 14.2.2.1.1](#) for mean RPI_{overall}
- [Table 14.2.2.2.1](#) for mean TPI_{overall}
- [Table 14.2.2.3.1](#) for mean RPI_{gingival margin}
- [Table 14.2.2.4.1](#) for mean RPI_{inter-proximal}
- [Table 14.2.2.5.1](#) for mean TPI_{inter-proximal}

Change from baseline of secondary efficacy variables will be analyzed using ANCOVA model with product group as a fixed effect and the appropriate baseline value as a covariate, as defined below:

- For mean RPI_{overall}: baseline mean RPI_{overall}
- For mean TPI_{overall}: baseline mean TPI_{overall} and RPI stratification level (lower/higher)
- For mean RPI_{gingival margin}: baseline mean RPI_{gingival margin}
- For mean RPI_{inter-proximal}: baseline mean RPI_{inter-proximal}
- For mean TPI_{inter-proximal}: baseline mean TPI_{inter-proximal} and RPI stratification level (lower/higher)

Change from Day 0 pre-brushing to each analysis time points (Visit 2 Day 0 post-brushing, Visit 3 Day 7 pre- and post-brushing and Visit 4 Day 28 pre- and post-brushing) will be summarized for each secondary outcome variable by product group (adjusted mean change, percent change from mean baseline, 95% CIs and p-value for change from zero) in the following analysis tables:

- [Table 14.2.2.1.2](#) for mean RPI_{overall}
- [Table 14.2.2.2.2](#) for mean TPI_{overall}
- [Table 14.2.2.3.2](#) for mean RPI_{gingival margin}
- [Table 14.2.2.4.2](#) for mean RPI_{inter-proximal}
- [Table 14.2.2.5.2](#) for mean TPI_{inter-proximal}

Percent change from mean baseline will be derived as: $100 \times (\text{Adjusted Mean Change} / \text{Mean Baseline Value})$. Adjusted Mean Change will be derived from ANCOVA model.

The assumption of normality and homogeneity of variance in the ANCOVA models will be investigated. Violation of this assumption will be overcome using a suitable data transformation or a non-parametric technique (e.g. Wilcoxon Sign Rank test).

Actual mean plaque scores (\pm SE) for all secondary efficacy endpoints will be plotted over time by study product group for all subjects in mITT population in the following figures:

- [Figure 14.2.2.1.1](#) for mean RPI_{overall}
- [Figure 14.2.2.2.1](#) for mean TPI_{overall}

-
- [Figure 14.2.2.3.1](#) for mean RPI_{gingival margin}
 - [Figure 14.2.2.4.1](#) for mean RPI_{inter-proximal}
 - [Figure 14.2.2.5.1](#) for mean TPI_{inter-proximal}

Pre-brushing values will be set at the nominal time recorded (Days 0, 7 and 28), while post-brushing values will be set at a small nominal time after (Days 0.5, 7.5 and 28.5).

All RPI index data collected in the eCRF will be listed in [Listing 16.2.6.1.2](#) for all randomized subjects while TPI index data collected in the eCRF will be listed in [Listing 16.2.6.2.2](#) for all randomized subjects.

The listings of derived scores of secondary efficacy variables by subject will be presented for all randomized subjects as follows:

- [Listing 16.2.6.1.1](#) for mean RPI_{overall}
- [Listing 16.2.6.2.1](#) for mean TPI_{overall}
- [Listing 16.2.6.1.3](#) for mean RPI_{gingival margin}
- [Listing 16.2.6.1.4](#) for mean RPI_{inter-proximal}
- [Listing 16.2.6.2.3](#) for mean TPI_{inter-proximal}

These listings will include subject number, visit, pre-brushing mean scores, post-brushing mean scores, change from pre-brushing to post-brushing, and change from Day 0 pre-brushing.

4.5.2 Pharmacokinetic (Secondary)

N/A

4.6 Analysis of Safety

All safety data will be reported for the Safety Population as per actual study product received. The safety profile of the study products will be assessed with respect to AEs, OST, OHT and incidents.

4.6.1 Adverse Events and Serious Adverse Events

All AEs will be reviewed by the Clinical Research Scientist or Designee prior to database lock and will be coded to a system organ class (SOC) and preferred term (PT) using the Medical Dictionary for Regulatory Activities (MedDRA).

AEs will be classified as oral and non-oral on the AE page of eCRF.

TEAEs are defined as an AEs that occur on or after the start date of first study product usage (if this date is missing a suitable alternative will be used e.g., date of randomization). AEs with an onset date/time prior to the first study product usage will be considered as non-treatment emergent.

The following summary tables and listings will be presented by study product group and overall:

- Table of TEAEs by SOC and PT ([Table 14.3.1.1.1](#)).
- Table of TEAEs by Oral/Non-Oral and PT ([Table 14.3.1.1.2](#)).

-
- Table of treatment-related TEAEs by SOC and PT ([Table 14.3.1.2.1](#)).
 - Table of treatment-related TEAEs by Oral/Non-Oral and PT ([Table 14.3.1.2.2](#)).
 - Table of treatment-emergent SAEs by SOC and PT ([Table 14.3.1.1.3](#)) [only produced if there are more than 5 SAEs].
 - Listing of all AEs ([Listing 16.2.7.1](#) for all randomized subjects; [Listing 16.2.7.2](#) for non-randomized subjects).
 - Listing of deaths ([Listing 14.3.2.1](#)).
 - Listing of non-fatal SAEs ([Listing 14.3.2.2](#)).
 - Listing of TEAEs leading to study or product discontinuation ([Listing 14.3.2.3](#)).
 - Listing of TEAEs classified as Oral ([Listing 14.3.2.4](#)).

In the event that there is nothing to report, a null table or listing will be produced.

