To evaluate the within-treatment supra-gingival plaque removal efficacy of four manual toothbrushes at the gingival margin and from inter-proximal sites, after single brushing events, following 0, 7 and 28 days familiarization with the brush.	
Change from baseline (Day 0 pre-brushing) to post-brushing in mean RPI and mean TPI - gingival margin sites (RPI only); inter-proximal sites (Day 0, Day 7, Day 28).
 
Pre- and post-brushing mean RPI and mean TPI - gingival margin sites (RPI only); inter-proximal sites (Day 0, Day 7, Day 28).

Objectives	Endpoints
To evaluate the within-treatment supra-gingival plaque removal efficacy of four manual toothbrushes after 7 and 28 days twice-daily brushing.	Change from baseline (Day 0 pre-brushing) in mean RPI and mean TPI - overall; gingival margin sites (RPI only); interproximal sites (Day 7 pre-brushing, Day 28 pre-brushing).
Safety	
To assess the safety and oral tolerability of the four manual toothbrushes after first use (Day 0) and over 28 days' use.	Treatment emergent adverse events (TEAEs)

Study Design

This will be a single center, 4-week, randomized, controlled, examiner-blind, four-treatment arm, parallel design, clinical methodology development study to investigate the plaque removal efficacy of marketed manual toothbrushes in healthy, dentate subjects. Changes in plaque level will be evaluated after first brushing, after two further single brushing events (Days 7 and 28) and following 7 and 28 days usage (twice daily brushing with assigned toothbrush treatment).

Supra-gingival plaque levels will be assessed using two established clinical measures: the Rustogi Modified Navy Plaque Index (RPI) and the 6-site Turesky Modified Quigley and Hein Plaque Index (TPI). Subjects will abstain from oral hygiene for a period of 12-18 hours prior to each assessment visit. Subjects with Day 0 pre-brushing mean RPI_{gingival/interproximal} \geq 0.6 will be stratified by their Day 0 pre-brushing RPI score (*lower*: mean RPI_{gingival/interproximal} \geq 0.6 to \leq 0.8; *higher*: mean RPI_{gingival/interproximal} $>$ 0.8 to 1.0) and randomized to study treatment (Visit 2).

To standardize oral hygiene practice, eligible subjects will complete a lead-in period (minimum 5 days) prior to Visit 2 during which they will brush with the toothbrush and regular fluoride toothpaste provided.

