4 STUDY DESIGN

4.1 Overall Design

This will be a single center, 4-week, randomized, controlled, examiner-blind, four-treatment arm, parallel design, clinical methodology development study to investigate the plaque removal efficacy of marketed manual toothbrushes in healthy, dentate subjects. Changes in plaque level will be evaluated after first brushing, after two further single brushing events (Days 7 and 28) and following 7 and 28 days usage (twice daily brushing with assigned toothbrush treatment).

Supra-gingival plaque levels will be assessed using two established clinical measures: the RPI and the TPI. Subjects will abstain from oral hygiene for a period of 12-18 hours prior to each assessment visit. Subjects with Day 0 pre-brushing mean RPI_{gingival/interproximal} ≥ 0.6 will be stratified by their Day 0 pre-brushing RPI_{gingival/interproximal} score (lower: mean RPI

gingival/interproximal ≥ 0.6 to ≤ 0.8 ; higher: mean RPI_{gingival/interproximal} > 0.8 to ≤ 1) and randomized to study treatment (Visit 2).

The mean RPI_{gingival/interproximal} ≥ 0.6 is calculated based on the 10 areas for inter-proximal & gingival margins (A, B, C, D, F – facial and lingual sites) as follow: RPI_{gingival/interproximal} sum score/number of gingival and interproximal sites.

To standardize oral hygiene practice, eligible subjects will complete a lead-in period (minimum 5 days) prior to Visit 2 during which they will brush with the toothbrush and regular fluoride toothpaste provided.

The safety and oral tolerability of each toothbrush will be monitored after first use and over the 28-day usage period by review of reported TEAEs.

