8.1.7 Dispensing/Supervised Use of Lead-In Toothbrush

Eligible subjects will be provided with lead-in toothbrush, regular fluoride toothpaste, diary and timer for use between Visits 1 and 2. Toothbrush usage instructions will be described to

the subject and site staff will supervise an on-site brushing with the lead-in toothbrush and completion of first use in the diary.

Spontaneous reporting of adverse events and those elicited by asking subjects to respond to a non-leading question such as “How do you feel?” will be assessed. Any AEs reported on completion of the supervised brushing will be recorded in the CRF.

Staff will remind subjects of the [Lifestyle Guidelines](#) and any [Concomitant Medication/Treatment\(s\)](#) requirements of the protocol before they leave the study site.

Completion of all procedures will be documented in the CRF.

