9.3.1 Oral Soft Tissue (OST) Examination

The OST examination will be accomplished by direct observation and palpation, using retraction aids as appropriate, and will include examination of the oral labial mucosa (including lips), buccal mucosa, and mucogingival folds, gingival mucosa, hard palate, soft palate, tonsillar area, pharyngeal area, tongue, sublingual area, submandibular area and salivary glands. The results of the examination will be recorded in the CRF as either normal or abnormal with details of any abnormalities. Any abnormality or worsening of a pre-existing condition observed by the clinical examiner or reported by the subject from the OST examination carried out at Screening will be recorded as an AE.

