10.6 Follow-up of Adverse Events

After the initial report, the investigator is required to proactively follow up with each subject and provide further information on the subject's condition.

All AEs (serious and non-serious) will be followed until resolution, until the condition stabilizes, until the event is otherwise explained, or until the subject is lost to follow-up.

The investigator is obligated to perform or arrange for the conduct of supplemental measurements and/or evaluations as may be indicated or as requested by GSK CH to elucidate as fully as possible the nature and/or causality of the AE. This may include additional laboratory tests or investigations, histopathological examinations, or consultation with other health care professionals.

New or updated information will be recorded on the AE CRF page and on the SAE form (subject to the classification of the AE).

The investigator will submit any updated SAE data to GSK CH within 24 hours of receipt of the information.

Investigators are not obliged to actively seek AEs in former subjects. However, if the investigator learns of a SAE, including death, at any time after a subject has been discharged from the study, and considers the event reasonably related to the study product or study participation, the investigator will promptly notify GSK CH by emailing the information to the GSK CH Clinical Operations Safety Reporting email box (PPD [REDACTED]

[REDACTED]). The GSK CH Study Manager or designee will be responsible for forwarding the information to the Case Management Group, Global Clinical Safety and Pharmacovigilance group mailbox at GSK (PPD [REDACTED]).

The investigator will submit any updated SAE data to GSK CH within the designated reporting time frames.

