Usage Instructions	Subjects will dose the toothbrush with a strip of regular fluoride toothpaste (full brush head) then brush their entire dentition for 1 timed minute, twice daily (morning and evening). On-site: Subjects will rinse with 10 mL tap water post-brushing for 5 seconds.			

	Off-site: Subjects will be permitted to rinse with tap water post-brushing, according to their normal habit.
Return Requirements	Used Samples: Destroy at site using site disposal procedures. Unused Samples: Return to 3 rd party vendor

Lead-in toothbrush **is not** considered as investigational/study product. All analysis described in this document will be based on 4 study toothbrushes.

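### The TEAE definition looks only at onset, so an adverse event that starts in the lead-in and worsens on the study brush is left out of the TEAE outputs unless the site enters the worsening as a new event

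*SAP*

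**What the plan says.** TEAEs are the only endpoint listed under the safety and oral tolerability objective (Protocol summary and Table 3-1; SAP Table 1-2). SAP 4.6.1 supplies the working definition in two sentences. The first includes: "TEAEs are defined as an AEs that occur on or after the start date of first study product usage". The second excludes: "AEs with an onset date/time prior to the first study product usage will be considered as non-treatment emergent". Neither mentions a change in intensity or seriousness.

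The reference point is first use of the assigned brush at Visit 2, because SAP 1.3 states: "Lead-in toothbrush is not considered as investigational/study product". Before that, Protocol 4.1 says that "eligible subjects will complete a lead-in period (minimum 5 days) prior to Visit 2", and footnote 1 to Table 1-1 sets no maximum. Adverse events are collected from consent (Protocol 10.3.1), including those seen at the first lead-in brushing: "Any AEs reported on completion of the supervised brushing will be recorded in the CRF" (Protocol 8.1.7).

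Three places in the protocol bear on worsening:
- Section 10.1 lists exacerbation of a chronic or intermittent pre-existing condition, in frequency or intensity, as meeting the adverse event definition.
- Section 9.3.1 treats a new abnormality, or the worsening of an existing condition, as an event when measured "from the OST examination carried out at Screening will be recorded as an AE". Section 9.3.2 does the same for hard tissue.
- Section 10.6, on follow-up of events already reported, says: "New or updated information will be recorded on the AE CRF page".

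**The concern.** The design puts every randomized subject through a run-in on a new brush and toothpaste, records adverse events throughout it, and then changes the brush. The lead-in brush is labelled ultra soft; three of the study brushes are labelled medium and one soft. Some events may therefore be open on the day the assigned brush is first used. If one of them becomes worse afterwards, the worsening happened on study product, yet a rule that looks only at onset assigns the event to the period before treatment.

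At stake is whether the sole listed safety endpoint captures that worsening. As written, this depends on how a site completes the CRF and not on a rule in the plan. Two sites, or two staff at this single site, could record the same clinical course in ways that put it inside or outside the TEAE tables. The loss could occur even if the investigator attributed the worsening to the brush, or if the subject stopped because of it, since the treatment-related tables and the discontinuation listing are also restricted to TEAEs.

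**Working it through.** The plan states no adverse event rate and no sample-size calculation, so there is no figure to reproduce. The check follows one case through the text: an oral event that starts in the lead-in, is ongoing at first use of the study brush, and rises in intensity by Day 7.

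1. **Is it recorded as an adverse event?** Yes. Collection starts at consent (Protocol 10.3.1), and the definition in 10.1 covers events on a lead-in product.
2. **How is that record classified?** Its onset precedes first study product use, so the SAP 4.6.1 exclusion sentence makes it non-treatment emergent, with no exception.
3. **Must the later rise in intensity become a new record?**
   - Protocol 10.6 says that updates go on the adverse event page. It does not say whether that means the same entry with the lead-in onset date or a new entry.
   - Protocol 10.1 makes exacerbation of a pre-existing condition an event and does not tie it to Screening. It could support a new entry. However, it speaks of chronic or intermittent conditions, and 10.3.1 sends occurrences that began before consent to medical history. An acute event first reported in the lead-in fits neither description cleanly.
   - Protocol 9.3.1 and 9.3.2 measure change from Screening. A finding that appeared in the lead-in already counts as an event on that comparison. Nothing says that further worsening makes a second one.
4. **Result.** If a new entry dated after first use is made, it is a TEAE. If the open entry is only updated, it is not. No text requires the first course.
5. **Which outputs lose it in the second case?** From the list in SAP 4.6.1:
   - TEAEs by SOC and PT, and by oral/non-oral and PT (Tables 14.3.1.1.1 and 14.3.1.1.2);
   - treatment-related TEAEs (Tables 14.3.1.2.1 and 14.3.1.2.2);
   - TEAEs leading to discontinuation (Listing 14.3.2.3);
   - oral TEAEs (Listing 14.3.2.4).
6. **Which outputs keep it?** Listing 16.2.7.1 covers all adverse events in randomized subjects. The listings of deaths and non-fatal SAEs are not restricted to TEAEs, should they apply.
7. **Does the soft tissue analysis recover it?** No. Table 14.3.4.2 compares normal/abnormal before and after brushing within each visit. Tissue that is abnormal before brushing and more abnormal afterwards shows no shift. Table 14.3.4.1 counts abnormalities but does not grade them.

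**Scale.** With about 80 subjects randomized to four arms, 80 / 4 = 20 per arm. One subject whose only oral event is lost this way changes that arm's oral TEAE incidence by 1 / 20 = 5 percentage points; two subjects change it by 2 / 20 = 10. The expected number would be 80 × (proportion with an event ongoing at first use) × (proportion of those that worsen) × (proportion not entered as new). The documents give none of the three proportions.

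**The case against.** The strongest reply is that the protocol already treats worsening as an adverse event. On that reading of section 10.1, the site enters the exacerbation with its own date, and it meets the SAP definition as written. Section 10.6 does not say otherwise, and conventions for splitting records normally sit in CRF completion guidance, which is not among the documents. This stands in part: exclusion is conditional, not certain. It does not remove the problem, because the SAP would then rely on a convention that neither document states.

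A reader might infer that the rule hides the tolerability effect of moving from an ultra-soft to a firmer brush. The documents do not support that. Soreness or abrasion that first appears after the change has its onset on study product and is counted in full. Only events already open at first use that then worsen are at risk. Visit 2 narrows this group further: a pre-brushing soft tissue examination and a review of eligibility come before randomization (Protocol 8.2.1), so some subjects with an ongoing oral problem may not be randomized.

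A reader might also want a count. Assuming that 5 to 15% of 80 subjects have an oral event ongoing at first use, and that 25 to 50% of those worsen, gives 80 × 0.05 × 0.25 = 1 to 80 × 0.15 × 0.50 = 6 subjects across the four arms. Neither rate has any support in the documents, so the range cannot be used as an estimate.

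Finally, this is a methodology study of marketed brushes with descriptive safety reporting, success is judged on plaque, and the events remain in the full listing. That limits the consequence, but it does not explain why the only listed safety endpoint should lack a rule for this case.

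**Conclusion.** The point holds in a limited form. SAP 4.6.1 states a rule based on onset alone with no worsening limb. An event that starts in the lead-in, is ongoing at first use and worsens on the study brush therefore leaves every TEAE table and TEAE listing unless the worsening happens to be entered as a new event. The conclusion rests on the current wording of SAP 4.6.1 and on the absence of any stated recording rule for an event already open; a rule in CRF guidance not supplied could close the gap in practice.

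The size is about 5 percentage points of a 20-subject arm per affected subject, assuming that the subject has no other event in the same category. The number of such subjects is unknown and probably small. It would be wrong to conclude that tolerability is generally overstated or that the events disappear from the report. The change is still worth making, because it corrects a stated rule for the sole listed safety endpoint at almost no cost.

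**What to change.** In SAP 4.6.1, define a TEAE as an adverse event with onset on or after first study product use, or one with earlier onset that increases in intensity on the mild/moderate/severe scale of Protocol 10.5.1, or becomes serious, after first use. Amend the exclusion sentence to match, so that only events with earlier onset and no such worsening are non-treatment emergent. The same edit can put both sentences on one clock: the inclusion sentence uses the date of first use and the exclusion sentence uses date and time, so they disagree about an event on Day 0 before the first brushing.

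Add one line to the CRF completion guidance requiring that such a worsening be recorded with its own date, so that the new limb can be programmed.

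The cost is one clause in the SAP, a matching edit to the next sentence, and one line of guidance. No visit, procedure or assessment is added. TEAE counts may be slightly higher. Using the Visit 2 pre-brushing soft tissue examination as a further comparator is not needed for this change.
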